## 10. Study Methods

### 10.1. *Data Collection*

There are a number of different study assessments required at each visit. The data collection schedule is provided in Table 11-1. Full descriptions for all assessments are provided in Section 12.

Table 10-1: Data Collection Schedule

	Screening	Medication Lock Visit	Period 1 Baseline Visit	Permanent Implantation	Period 1		Period 1 Interim Visit		End of Period 1 Visit		Period 2		Period 2 Interim Visit		End of Period 2 Visit		End of Study Visit	
					(Day 0)	(30 days)	(0-7 days post Baseline)	(0-14 days post Baseline)	(0-14 days post-Period 1 Baseline)	(Day 0)	(15 days)	(Day 0)	(21 days ± 7)	(45 days ± 7)	(59 days ± 7)	(365 ± 30 days)		
Adverse Event (AE)			X	X	X	X	X	X	X	X	X	X	X	X	X	X	X	X
Beck Depression Inventory (BDI-II)									X								X	X
Columbia Suicide Severity Rating Scale (C-SSRS)									X								X	X
Concomitant Medications			X				X		X			X				X	X	X
Demography									X								X	X
Electronic Diary (eDiary)																		
EQ-5D 5 Level (EQ-5D-5L)																		
Inclusion/Exclusion Criteria Evaluation																		
Informed Consent (ICF)																		
Long-Term Therapy Selection (LTS)																		
Medical History																		
Neurological Assessment																		
Oswestry Disability Index version 2.1a (ODI v2.1a)																		
Pain Intensity																		
Patient Global Impression of Change (PGIC)																		
Percent Pain Relief (PPR)																		
Physical Exam																		
Pittsburgh Sleep Quality Index (PSQI)																		
Post-Operative Evaluation																		
Procedure Information																		
Programming Parameters																		
Resource Utilization Inventory (RUI)																		
Short Form Health Survey 36 item (SF-36v2)																		
Short Form McGill Pain Questionnaire (SF-MPQ-2)																		
Stimulation Sensation Questionnaire (SSQ)																		
Treatment Satisfaction Questionnaire (TSQ-M-Sm)																		
Work Productivity & Impairment (WPAI-SHP V2.0)																		

\*Last programming until the End of Period Visit.

\*\*For unscheduled visits where procedures are performed.

\*\*\*Only when device programming is performed.

Opioid Medications Locked

### **10.2. Study Candidate Screening (Up to 60 days following Informed Consent)**

Inclusion and Exclusion criteria listed in Sections 9.2 and 9.3, respectively, will be assessed to determine study candidate eligibility. Screening is a process that includes criteria being assessed from the time of informed consent through the Period 1 Baseline Visit. The 60 day window for screening reflects the maximum timeframe from which a patient can be consented and for screening activities to begin prior to completing the medication lock visit. Subjects who have provided informed consent and who have been determined to not meet all eligibility requirements prior to randomization will be withdrawn.

[figure not shown]
### **10.3. Informed Consent**

Written Informed Consent must be obtained for all patients who are potential study candidates. Study candidates will be asked to sign the Informed Consent form before any study-specific tests or procedures are performed. The context of the study must be fully explained to the study candidate in language that is easily understood by the study candidate. Study candidates must also be given the opportunity to ask questions and have those questions answered to their satisfaction. The Informed Consent form is study-specific and must be approved by the site Institutional Review Board (IRB). Study personnel should explain that even if a study candidate agrees to participate in the study and signs an Informed Consent form, certain diagnostic or screening procedures might demonstrate that the study candidate is not eligible to continue participation.

Research study candidates in the State of California will also be provided with the California Experimental Patient's Bill of Rights.

#### **10.3.1. Post-Consent Eligibility Validation**

After obtaining written informed consent, the following tests may be conducted to evaluate study-specific eligibility criteria. Study candidates not meeting the eligibility criteria will be withdrawn:

Subjects taking prescription opioids for primary chronic pain complaint (low back and/or leg pain) whose pain medications are not stable for 30 days following informed consent will be withdrawn however may be reconsented and rescreened once 30 days have passed.

#### **10.4. Medication Lock Visit**

The Medication Lock Visit will occur after completion of screening requirements as described in Section 10.2. At this visit, subjects' opioid medications will be locked (no change in type/dose/route) and will remain unchanged until End of Period 2 visit.

- **Visit Type:** In-office
- **Required Attendees:** Subject; Clinical Research Coordinator (CRC) and/or Investigator
- **Study Assessments:** All required visit assessments, as outlined in Table 11-1, should be performed.
- **Medications:** During the screening period or at this visit, the investigator will convert the subject's opioid medication prescriptions from PRN to a fixed dose, as needed. Subjects will be reminded not to make any changes to their opioid medications (type/dose/route) through End of Period 2 Visit and record their opioid medication use daily, as directed by the eDiary. The details regarding protocol medication requirements are summarized in Section 11.22.
- **eDiary:** At the end of this visit subjects will be given an eDiary for daily use during the Baseline period through the End of Period 2 Visit. The eDiary will collect information regarding subjects' pain intensity, medication and device charging compliance (after permanent implantation) and subjects will be instructed on the use of the eDiary. The details regarding the information collected in the eDiary is summarized in Section 13.1.1

#### **10.5. Period 1 Baseline**

Period 1 baseline will last for 30 consecutive days following the Medication Lock visit. During this period, subjects will be asked to answer all questions on the eDiary daily for 30

Page 60 of 177

consecutive days beginning with the first entry the day following receipt of the eDiary. Subjects will return to the clinic with their eDiary for the Period 1 Baseline Visit.

#### ***10.6. Period 1 Baseline Visit (0-7 days post Period 1 Baseline)***

[figure not shown]
At the Period 1 Baseline Visit, subjects will return to the office with their eDiary to evaluate their continuing eligibility in the study. Subjects that meet all study criteria will be scheduled for the device implant procedure. If subjects fail to meet all the eligibility criteria, they will be withdrawn from the study.

- **Visit Type:** In-office
- **Required Attendees:** Subject; CRC and/or Investigator
- **Study Assessments:** All required visit assessments, as outlined in Table 11-1, should be performed at the beginning of the visit.
- **eDiary:** All eDiary inclusion and exclusion criteria will be evaluated by the investigator. Subject's compliance to the fixed opioid dose will also be assessed. Subjects who do not meet required inclusion/exclusion criteria will be withdrawn. The eDiary will be reviewed during the visit and all eligible subjects will be instructed to continue completing their eDiary daily.
- **End of Visit Information:** Subjects should be reminded not to make any changes to their opioid medications (type/dose/route) and record their opioid medication use daily, as directed by the eDiary.

#### ***10.7. Permanent Implantation (0-14 days Post Period 1 Baseline Visit)***

Subjects have up to 14 days to receive their Precision SCS System implant. All subjects in this study will proceed directly to permanent implantation and not undergo a screening trial. Subjects where implant procedure was unsuccessful will be withdrawn from the study as summarized in Section 9.2.

- **Visit Type:** Procedure
- **Required Attendees:** Subject; CRC and/or Investigator; Field Clinical Engineer/Field Clinical Specialist or designee
- **Study Assessments:** All required visit assessments, as outlined in Table 11-1, should be performed.
- **eDiary:** The eDiary will be reviewed and updated as needed (e.g. addition of new acute opioid medications for procedural discomfort) during the visit and subjects will be instructed to continue completing their eDiary daily.

- **Programming Requirements:** The IPG may be programmed but, following the completion of programming, the device will be OFF until the Period 1 Activation Visit.
- **Acute Opioid Pain Medication:** The use of acute opioid pain medication for procedural discomfort is allowed, per site's routine care.
- **End of Visit Information:** Following the implant procedure, instructions related to follow up care will be provided.
  - Subjects are to contact the site in an event that any additional intervention is warranted, to report a suspected adverse event, etc.
  - Subjects should be reminded not to make any changes to their opioid medications (type/dose/route) and to record their opioid medication use daily, as directed by the eDiary.
  - If device implantation is unsuccessful, subjects will be followed for 2 weeks post implantation in an attempt to assess for procedure related adverse events, if they occur.

#### **10.8. Healing Period (7-14 days)**

The subject's device will remain inactivated (device OFF) for 7-14 days following the permanent implantation procedure to allow for healing. Acute opioid pain medications may be taken during this period. No additional scheduled assessments will be completed during this period. Subjects will continue to complete their eDiary daily during this period.

Page 62 of 177

### 10.9. Period 1 Activation Visit (Period 1 Day 0)

Subjects' device will be activated at the Period 1 Activation Visit based on their treatment assignment. Subjects will be randomized (1:1) to either receive High Rate or Commercial Rate settings at this visit.

- **Visit Type:** In-office
- **Required Attendees:** Subject; CRC and/or Investigator; Field Clinical Engineer/Field Clinical Specialist or designee
- **Randomization:** Randomization must occur at the start of visit and prior to device activation at the Period 1 Activation Visit.
- **Study Assessments:** All required visit assessments, as outlined in Table 11-1, should be performed.
- **eDiary:** The eDiary will be reviewed during the visit and subjects will be reminded to continue to complete their eDiary daily.
- **Device Programming:** To aid in programming it is recommended that Anterior/Posterior thoracic and lumbar imaging (e.g. x-ray or fluoroscopy) is obtained at this visit or up to 7 days prior to the visit to show the position(s) of the study device lead(s). The IPG will be activated using one or more programs created strictly in accordance with Section 10.22.1 for the Period 1 assignment based on their treatment assignment. Final program settings must be documented in the study records. In the event of suspected lead migration, imaging may be performed to document lead positions.
- **Acute Opioid Pain Medication:** The continued use of acute opioid pain medication for procedural discomfort is not allowed following the Period 1 Activation Visit.
- **End of Visit Information:** Subjects should receive instructions on the use of the device including Remote control and charging system.
  - Subjects are to contact the site in an event that any additional intervention is warranted, to report a complaint and/or a suspected adverse event, reprogramming, etc.
  - Subjects should be instructed to evaluate all programs saved on the remote control prior to their next visit.
  - Subjects should be reminded to charge their Precision SCS system daily until charging is complete (charger double-beeps). It is recommended that they check the status of their battery using their remote control.
  - Subjects should be reminded not to make any changes to their opioid medications (type/dose/route) and to record their opioid medication use daily, as directed by the eDiary.

Subjects may have as many unscheduled visits as required for optimization of programming prior to mid period visit, as long as programming is done in accordance with Section 10.22.

Page 63 of 177

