## **7. Design**

The study is a multi-center, randomized, controlled, non-inferiority, crossover, adaptive, open label design. In this crossover design, eligible subjects will be randomized in a 1:1 ratio to receive one of the following sequences:

- CR-SCS followed by HR-SCS
- HR-SCS followed by CR-SCS

using the Boston Scientific PRECISION™ SCS System and the Boston Scientific PRECISION SCS System for HR. The study is open label, thus the study participants, investigative site personnel, and the sponsor will not be blinded. All subjects will undergo permanent system implantation. The study design is shown in Figure 7-1.

[REDACTED]

[REDACTED]

Confidential

Protocol Template  
ACCELERATE Study

Page 40 of 177

[figure not shown]

Figure 7-1. ACCELERATE Study Design

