### ***7.2. Treatment Assignment***

Eligible subjects will be randomized in a 1:1 ratio to receive one of the following sequences:

- CR-SCS followed by HR-SCS
- HR-SCS followed by CR-SCS

Randomization will be implemented in the Electronic Data Capture (EDC) system using a pre-generated randomization table. Random permuted blocks stratified by site will be employed to ensure approximate balance of treatment allocation.

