### ***9.3. Subject Status and Classification***

Subjects who provide written informed consent but do not meet all of the study eligibility criteria will not be implanted and randomized. These subjects will be deemed as “enrolled but not randomized” and their reason for ineligibility will be documented in the EDC system. Enrolled subjects who are not randomized will not count towards the enrollment cap. Subjects who sign consent, meet all eligibility criteria, and are randomized cannot be replaced.

[REDACTED]

[REDACTED]

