#### **10.15. *Period 2 Baseline/Activation Visit (0-7 days post Period 2 Baseline, Period 2 Day 0)***

Subjects' baseline data for Period 2 will be collected at the start of this visit. Subjects' device will be programmed based on their treatment assignment for the remainder of Period 2. The device must be activated only after completion of required assessments for this baseline visit. Subjects should continue to complete their eDiary with no changes to their opioid medications.

- **Visit Type:** In-office
- **Required Attendees:** Subject; CRC and/or Investigator; Field Clinical Engineer/Field Clinical Specialist or designee
- **Study Assessments:** All required visit assessments, as outlined in Table 11-1, should be performed.
- **eDiary:** The eDiary will be reviewed during the visit and subjects will be reminded to continue to complete their eDiary daily

Page 66 of 177

- **Device Programming:** To aid in programming it is recommended that Anterior/Posterior thoracic and lumbar imaging (e.g. x-ray or fluoroscopy) is obtained at this visit or up to 7 days prior to the visit to show the position(s) of the study device lead(s). The IPG will be activated using one or more programs created strictly in accordance with Section 11.21.2 for the Period 2 assignment. Final program settings must be documented in the study records. In the event of suspected lead migration, imaging may be performed to document lead positions.
- **End of Visit Information:** Subjects should receive instructions on the use of the device including Remote control and charging system.
  - Subjects are to contact the site in an event that any additional intervention is warranted, to report a complaint and/or a suspected adverse event, reprogramming, etc.
  - Subjects should be instructed to evaluate all programs saved on the remote control prior to their next visit.
  - Subjects should be reminded to charge their Precision SCS system daily until charging is complete (charger double-beeps). It is recommended that they check the status of their battery using their remote control.
  - Subjects should be reminded not to make any changes to their opioid medications (type/dose/route) and to record their opioid medication use daily, as directed by the eDiary.

Subjects may have as many unscheduled visits as required for optimization of programming prior to mid period visit, as long as programming is done in accordance with Section 10.22.

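### Section 10.9 randomises at the start of the Period 1 Activation Visit, so that visit's assessments follow with the open-label assignment known, and a subject then found unfit for activation is already in ITT

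*Combined protocol and SAP*

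**What the plan says.** Section 10.9 fixes the moment of randomisation: "Randomization must occur at the start of visit and prior to device activation at the Period 1 Activation Visit". It then lists the visit's work without ordering it against randomisation. On assessments it says "All required visit assessments, as outlined in Table 11-1, should be performed" (the schedule itself is numbered Table 10-1). Diary review and device programming follow. Lead imaging is recommended, not required, and its timing is flexible: it "is obtained at this visit or up to 7 days prior to the visit".

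Section 7 removes any concealment after assignment: "The study is open label, thus the study participants, investigative site personnel, and the sponsor will not be blinded".

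On who is counted, section 11.6.1 puts every randomised subject in ITT, with no condition that the device was switched on, and leaves out implanted subjects who withdraw before being randomised. Section 9.3 adds: "Subjects who sign consent, meet all eligibility criteria, and are randomized cannot be replaced". Under section 10.21, a subject who declines a recommended lead revision is withdrawn but kept in ITT, and one who accepts continues on the schedule already set.

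**The concern.** Two things follow from randomising first.

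The first is avoidable knowledge of assignment. Section 10.8 schedules no assessments during healing, so this visit is the next planned contact after implant. Adverse events are collected from consent and classified by relationship to device and procedure (12.2.1). Events since implant that come to light at this visit arose with the device off, so they cannot depend on HR or CR stimulation, yet staff would judge them knowing which was assigned. An open-label design makes such knowledge unavoidable after activation, but not before it.

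The second is avoidable non-starters. If the visit reveals a reason not to activate, such as a migrated lead, the subject is already committed to ITT and may contribute no Period 1 therapy or a shortened one. In a non-inferiority comparison, subjects untreated under both labels tend to draw the two therapies together, which favours the claim.

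**Working it through.** The plan gives no figure on this point to reproduce. The check sets the sections side by side and adds one illustration.

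**1. Order within the visit.** Section 10.9 places randomisation at the start. Nothing in it says that assessments come first, so the natural reading is randomisation, then assessments and diary review, then programming. Imaging is different: it may precede the visit by up to 7 days, so only imaging done on the day itself would follow randomisation.

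**2. Which data can be affected.** Section 7.4 takes the primary-endpoint baseline from diary entries in the 15 days before the Baseline Visit. Sections 10.6 and 10.7 put that visit before implant, and section 10.9 puts randomisation after implant and healing. The Period 1 baseline is therefore complete before anyone knows the assignment. The 3-month outcome is unblinded whatever the order within this visit. What remains exposed is the visit's own assessments, chiefly safety. Exactly which ones these are cannot be confirmed, because the schedule table is not legible in the available text.

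**3. Who enters ITT.** Unsuccessful implants are withdrawn at the implant stage (10.7), and withdrawals before randomisation fall outside ITT (11.6.1). The subjects at issue are therefore only those who reach this visit, are randomised, and are then found not to be activatable.

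**4. Illustration of dilution.**
- Inputs: the margin of 0.10 (11.1.1), and *f*, the fraction of randomised subjects never activated. The documents do not give *f*, so it is an assumption shown over a range.
- Further assumption: these subjects are scored as zero response under both therapies.
- Formulas: observed ITT difference = (1 − *f*) × true difference; effective margin = 0.10 / (1 − *f*).

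| *f* | Observed difference when the true deficit is 0.10 | Effective margin |
|---|---|---|
| 0% | 1.00 × 0.10 = 0.100 | 0.10 / 1.00 = 0.100 |
| 1% | 0.99 × 0.10 = 0.099 | 0.10 / 0.99 = 0.101 |
| 2% | 0.98 × 0.10 = 0.098 | 0.10 / 0.98 = 0.102 |
| 5% | 0.95 × 0.10 = 0.095 | 0.10 / 0.95 = 0.105 |
| 10% | 0.90 × 0.10 = 0.090 | 0.10 / 0.90 = 0.111 |

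A subject whose therapy is delayed rather than absent would dilute less. The effect on type I error cannot be computed, because sample size and variance are not readable.

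**The case against.** The strongest reply is that this is a matter of order within one visit of an openly unblinded trial, with no demonstrated effect on the primary result. Much of that stands. The plan already randomises late, after implant and healing. Keeping every randomised subject in ITT is correct practice. All primary and secondary endpoints are also analysed per protocol (11.6), although the readable text does not say whether non-activation counts as a major deviation. The scoring of never-activated subjects may sit in redacted text in section 11.9, so the direction of any dilution rests on a rule that cannot be seen.

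A reader might infer three stronger points that the documents do not support:
- *That randomisation is required before lead imaging.* It is not. Section 10.9 allows imaging in the preceding 7 days, so a site can detect a migrated lead before randomising.
- *That the Period 2 visit shows the sponsor protecting assessments from knowledge of assignment.* Section 10.15 does say "The device must be activated only after completion of required assessments for this baseline visit", but that orders assessments against activation. Subjects are randomised once, to a sequence (7.2), so the Period 2 therapy is known well before that visit. The order there keeps stimulation off while a new baseline is taken.
- *That the primary endpoint's baseline is biased.* It predates randomisation.

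The objection also raises a fair caution about the remedy. A discretionary check before randomisation, with permuted blocks within site and no blinding, gives staff some room to select when the next assignment can be guessed. Block size is not readable, so the extent is unknown. This argues for objective, recorded criteria rather than against the change.

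**Conclusion.** The concern holds in a limited form. Section 10.9 creates knowledge of assignment during pre-stimulation assessments, and possible post-randomisation non-starters, both of which a later point in the same visit would avoid. This rests on reading the start of the visit as coming before the assessments, which is the natural reading but is not spelled out.

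The size is small. The primary baseline is unaffected. Under the zero-response assumption, a true deficit at the margin would shrink from 0.10 to between 0.099 and 0.090 for non-activation of 1% to 10%. The actual rate is unknown, so no specific dilution can be claimed. No change to sample size or alpha follows. This is a cheap improvement to conduct.

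**What to change.** Amend section 10.9 so that randomisation in the EDC takes place at the same visit, after the required assessments, the diary review, the review of any imaging and the device check have been completed and recorded, and immediately before programming and activation. Require any reason for not randomising at that point to be documented against objective criteria set in advance by the sponsor. If a redacted section does not already do so, state how subjects who are randomised but never activated are scored in the ITT and per-protocol analyses.

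The cost is a sentence or two in the protocol and a change of form order in the EDC, with the same visit and the same staff. Programming staff learn the assignment slightly later, and the pre-randomisation check must be objective. Safety data are not lost, because the safety set (11.6.3) includes everyone who signed consent, whether or not they were randomised.
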